# 6.1.7. ECG Telemetry

Subjects will be monitored by telemetry as outlined in Table 6-1. To allow a real-time assessment of cardiac safety (HR, rhythm, and ECG morphology) at the CRU, subjects will be monitored at least by 2-lead telemetry. Telemetry monitoring will be performed on Day -1 (starting approximately 24 hours before the start of morphine IV infusion) until 72 hours after the end of morphine IV infusion (Day 4), on Day 7 at least 30 minutes prior to AZD4041 or placebo dosing until 48 hours post Day 7 dose (Day 9), and on Day 15 at least 30 minutes before the start of morphine IV infusion (Day 18). Any clinically significant change noted on telemetry will be followed up with a 12-lead safety ECG. Further evaluation including any treatment will be performed as deemed appropriate by the Investigator. Any finding of short, self-limiting, asymptomatic arrhythmia (eg, non-significant supraventricular tachycardia, atrial fibrillation or flutter, ventricular extrasystoles, ventricular tachycardia), should be documented and further evaluated in the context of the individual subject's history and clinical status. Irrespective of the intervention,

cardiac monitoring will be continued until an observed event resolves or the subject is deemed clinically stable by the Investigator.

# 6.1.8. Continuous and Spot Oxygen Saturation

Assessments will include continuous and spot SpO2 monitoring, as scheduled in Table 6-1. Continuous and spot SpO2 will be monitored using a capnography monitor except for the spot SpO2 at Screening, Day -2, and Follow-up visit/ET which will use a portable pulse oximeter placed on the subjects' fingertip. SpO2 will be continuously monitored for alarms from at least 1 hour prior to each study drug administration (prior to start of morphine IV infusion on Day 1 and Day 15) and will continue for up to 6 hours following each study drug administration (after the end of morphine IV infusion on Day 1 and Day 15), or longer if deemed medically necessary. Spot SpO2 will be documented as scheduled in Table 6-8. Baseline SpO2 will be determined at 6 timepoints predose on Day 1. The baseline value will be determined by averaging the 6 readings.

Table 6-8	Spot Oxygen Sa	aturation Recording Schedule
Smat Omeran	Saturnation Deconding	Sahadalad Timon sin4a

pot Oxygen Saturation Recording - Scheduled Timepoints
Screening
Day -2
Day 1: predose (at -60, -50, -40, -30, -20, and -10 minutes) and 15, 30 minutes and 1, 1.5, 2, 3, 4, 6, 8, and 12 postdose
Days 2 to 7: predose
Day 8: predose and 15, 30 minutes and 1, 1.5, 2, 3, 4, 6, 8, and 12 hours postdose
Days 9 to 14: predose
Day 15: predose and 15, 30 minutes and 1, 1.5, 2, 3, 4, 6, 8, 12, and 24 hours postdose
Follow-up visit/ET
bbreviation: ET = Early Termination

Abbreviation: ET = Early Termination

Note: On Day 1 and Day 15, predose time points are relative to start of morphine infusion and postdose time points are relative to end of morphine infusion.

The acceptable windows for spot SpO2 recording are presented in Table 6-9.

Table 0-9	Acceptable windows for Sp	O2 Assessments 1 roceuures
	Elapsed Time	Accepted Window
	$\geq$ -1 hour and < 1 hour	$\pm 10$ minutes
	$\geq$ 1 hour and $\leq$ 24 hours	$\pm$ 30 minutes

Tabla 6 0 Accentable Windows for SnO2 Assessments Procedures

## 6.1.9. Continuous and Spot End-Tidal Carbon Dioxide

End-tidal carbon dioxide (EtCO2) will be monitored and measured using a standardized methodology and configuration using MICROSREAMTM consumables to sample gas via nasal cannulae and the CAPNOSTREAMTM20P bedside monitor according to Altasciences SOP on Capnography (CLS-5105-00, September 1st 2020). Using this configuration, for the spontaneously breathing healthy volunteer subject, baseline EtCO2 measurements can be

expected to fall within the range 34-48 mmHg. Measurement of EtCO2 has been applied successfully in the setting of clinical pharmacology studies for the evaluation of respiratory function (Viscusi et al, 2021). Historical data sets generated at the Altasciences clinical unit have recorded EtCO2 values with acceptable variability in relatively small cohorts of healthy volunteer subjects. For example, in a cohort of N=8 subjects, mean baseline EtCO2 was found to be 36.6 mmHg with SD 2.2 mmHg. In another cohort of N=15 subjects, mean baseline EtCO2 was found to be 36.1 mmHg with SD 3.88 mmHg.

Assessments will include continuous and spot EtCO2 through a capnography monitor, as scheduled in Table 6-1. EtCO2 will be monitored continuously for alarms at least 1 hour prior to each study drug administration (prior to start of morphine IV infusion on Day 1 and Day 15) and will continue for up to 6 hours following each study drug administration (after the end of morphine IV infusion on Day 1 and Day 15), or longer if deemed medically necessary. Spot EtCO2 will be recorded as scheduled in Table 6-10. Baseline EtCO2 will be determined at 6 time points predose on Day 1. The baseline value will be determined by averaging the 6 readings.

# Table 6-10Spot End-Tidal CO2 Recording ScheduleSpot End-Tidal CO2 Recording - Scheduled Timepoints

Day 1: predose (at -60, -50, -40, -30, -20, and -10 minutes) and 15, 30 minutes and 1, 1.5, 2, 3, 4, 6, 8 and 12 postdose

Days 2 to 7: predose

Day 8: predose and 15, 30 minutes and 1, 1.5, 2, 3, 4, 6, 8 and 12 hours postdose

Days 9 to 14: predose

Day 15: predose and 15, 30 minutes and 1, 1.5, 2, 3, 4, 6, 8, 12 and 24 hours postdose

Note: On Day 1 and Day 15, predose time points are relative to start of morphine infusion and postdose time points are relative to end of morphine infusion.

The acceptable windows for EtCO2 assessments are presented in Table 6-11.

Table 6-11	Acceptable Windows for EtCO 2 Assessments Procedures
------------	---

Elapsed Time	Accepted Window
$\geq$ -1 hour and < 1 hour	$\pm 10$ minutes
$\geq$ 1 hour and $\leq$ 24 hours	$\pm$ 30 minutes

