## 3. STUDY DESIGN

#### **3.1. Overall Study Design**

This is a Phase 1, randomized, double-blind, placebo-controlled, 2 fixed sequences, multiple dose study in healthy male and/or female recreational opioid users.

This study will consist of 3 phases: Screening and Qualification, Treatment phase, and Follow-up (see Figure 3-1).

After a Screening period of up to 27 days (Day -30 to Day -3), eligible subjects will be admitted to the clinical research unit (CRU) on Day -2. Subjects will be randomized to 1 of 2 fixed treatment sequences (28 subjects in Sequence 1, and 16 subjects in Sequence 2) on Day -1.

Subjects will be required to present a negative urine drug and alcohol screen upon admission on Day-2, except for tetrahydrocannabinol (THC). If THC is positive at admission, a cannabis intoxication evaluation will be done by an Investigator, and subjects may be permitted to continue in the study at the discretion of an Investigator. Subjects will then undergo a naloxone challenge where an initial 0.2 mg intravenous (IV) dose of naloxone hydrochloride (HCl) will be administered. The subject will be observed for signs or symptoms of opioid withdrawal. If there is no evidence of withdrawal within 1 minute (as assessed by a Clinical Opioid Withdrawal Scale [COWS] score of <5), an additional 0.6 mg IV dose of naloxone HCl will be given, and the subject will be observed for signs and symptoms of withdrawal for 5 minutes (as assessed by COWS). Subjects who present symptoms of withdrawal during the qualification process will be excluded from the study and will not be eligible to enter the Treatment phase.

In total, subjects will be confined to the CRU for approximately 20 days from Day -2 to Day 18 (until approximately 72 hours following the last study drug administration).

On Day 1, subjects will receive a single CCI IV dose of morphine. From Day 2 to Day 15, subjects will receive a CCI oral dose of AZD4041 or placebo once daily for 14 consecutive days. On the morning of Day 15, the CCI oral dose of AZD4041 or placebo will be combined with a single CCI IV dose of morphine.

In order to limit the number of subjects being treated with investigational product (IP) on any single day, eligible subjects should be assigned to different subgroups. Subgroup sizes should be limited to no more than 8 subjects. Dosing of subgroups should be staggered to occur on different days, with at least 2 days between the start of dosing for sequential subgroups.

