### **3.2. Study Treatments**

The following treatments will be administered according to Table 3-1.

- Test: A single CCI of AZD4041 oral solution will be administered once daily from Day 2 to Day 15 according to the randomization schedule.
- **Placebo**: Vehicle without active drug (AZD4041) will be orally administered once daily from Day 2 to Day 15 according to the randomization schedule.
- Morphine: A CCI administered on Days 1 and Day 15 only.

of morphine will be intravenously

Table 3-1	Treatment Sequences		
	Day 1	Days 2 to 14	Day 15 a
Sequence 1 (n=28)	CCI Morphine	CCI AZD4041 once daily	CCI AZD4041 + CCI Morphine
Sequence 2 (n=16)	CCI Morphine	Placebo once daily	Placebo + CCI Morphine

a. The assigned treatment (AZD4041 or Placebo) will be administered orally immediately (within 1 minute) after the end of morphine infusion.

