# Table 6-12 Spot Respiratory Rate Recording Schedule

Spot Respi	iratory rate Recording - Scheduled Timepoints
Screen	ing
Day -2	
•	predose (at -60, -50, -40, -30, -20, and -10 minutes) and 15, 30 minutes and 1, 1.5, 2, 3, 4, 6, 8 postdose
Days 2	2 to 7: predose
Day 8:	predose (within 60 minutes) and 15, 30 minutes and 1, 1.5, 2, 3, 4, 6, 8 and 12 hours postdose
Days 9	to 14: predose
Day 15 postdos	5: predose (within 60 minutes) and 15, 30 minutes and 1, 1.5, 2, 3, 4, 6, 8, 12 and 24 hours se
Follow	/-up visit/ET

Abbreviation: ET = Early Termination

Note: On Day 1 and Day 15, predose time points are relative to start of morphine infusion and postdose time points are relative to end of morphine infusion.

The acceptable windows for respiratory rate assessments are presented in Table 6-11.

Table 6-13	Acceptable Windows for Respiratory Rate Assessments Procedures

Elapsed Time	Accepted Window
$\geq$ -1 hour and < 1 hour	$\pm 10$ minutes
$\geq 1$ hour and $\leq 24$ hours	$\pm$ 30 minutes

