For EtCO₂, SpO₂, and respiratory rate the following figures will be generated:

- 1) Sequence 1: Mean (\pm SD) treatment by time point for Day 1 Morphine alone matched to Day 15 Morphine + AZD4041
- 2) Sequence 2: Mean (\pm SD) treatment by time point for Day 1 Morphine alone matched to Day 15 Morphine + Placebo
- 3) Mean (\pm SD) treatment by time point for Days 2-15 predose AZD4041 vs. Days 2-15 predose Placebo
- 4) Boxplot for E_{max} Day 1 Morphine alone matched to Day 15 Morphine + AZD4041
- 5) Boxplot for E_{max} Day 1 Morphine alone matched to Day 15 Morphine + Placebo
- 6) Boxplot for E_{max} Day 15 Morphine + AZD4041 vs. Day 15 Morphine + Placebo

For all inferential analysis on EtCO₂, SpO₂, and respiratory rate, mixed-effects models will be used for E_{max} and averaged measures. The models will include sequence, time (as a ordered factor variable), and the sequence-by-time interaction as fixed effects and baseline as a covariate, with 95% confidence intervals reported along with p-values. Homogeneity of treatment variances will be explored to determine if subject may be considered a random effect. The covariance structure for the mixed models will be heterogeneous compound symmetry. If the heterogeneous compound symmetry model does not converge, then a compound symmetry structure will be used and a footnote will be added to identify the results as using a different covariance structure than usual. The kenwood-roger adjustment for the degrees of freedom will be used when calculating p-values due to the small sample size.

The maximum postdose decrease in respiratory rate (E_{max (predose - postdose)}) is the primary criterion. In addition to the primary criterion, maximum postdose reduction in SpO₂ (E_{max (predose - postdose)}) and The maximum postdose increase in EtCO₂ (E_{max (postdose - predose)}) will have the following contrasts calculated in the mixed-effects models:

- 1) Morphine + AZD4041 (Day 15) vs Morphine alone (Day 1) [Sequence 1]
- 2) Morphine + Placebo (Day 15) vs Morphine alone (Day 1) [Sequence 2]
- 3) Morphine + AZD4041 (Day 15) vs Morphine + Placebo (Day 15) [Sequence 1 vs Sequence 2]

For EtCO₂, SpO₂, and respiratory rate averages (predose average from Days 2 to 15), and postdose average on Day 15, the following contrasts will be explored in the mixed-effects models:

- 1) (postdose): Morphine + AZD4041 (postdose average Day 15) vs (predose): AZD40401 (predose average Days 2-15)

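### The AZD4041 predose average over Days 2 to 15 includes the Day 2 reading, taken before any AZD4041; start it at Day 3

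*Protocol*

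**What the plan says.** **Predose average.** SAP 9.1 lists mixed-model contrasts for EtCO2, SpO2 and "respiratory rate averages (predose average from Days 2 to 15), and postdose average on Day 15". The first compares the Day 15 postdose average on morphine plus AZD4041 with the AZD4041 predose average over Days 2 to 15. The second compares that predose average between the AZD4041 and placebo arms. Protocol 8.3.2.1 has the same two contrasts.

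**Dosing.** Protocol 3.1 states: "From Day 2 to Day 15, subjects will receive a CCI oral dose of AZD4041 or placebo once daily for 14 consecutive days". Protocol 3.2 agrees: AZD4041 "will be administered once daily from Day 2 to Day 15 according to the randomization schedule". Morphine is given on Days 1 and 15 only, and Protocol 5.3 places all dosing in the morning.

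**Spot readings.** Table 6-10 (EtCO2) schedules "Days 2 to 7: predose", then a predose reading on Day 8, on Days 9 to 14 and on Day 15. Tables 6-8 (SpO2) and 6-12 (respiratory rate) follow the same predose pattern. After morphine on Day 1, Table 6-10 has "15, 30 minutes and 1, 1.5, 2, 3, 4, 6, 8 and 12 postdose"; its Day 15 line adds a reading at 24 hours: "Day 15: predose and 15, 30 minutes and 1, 1.5, 2, 3, 4, 6, 8, 12 and 24 hours postdose". Table 6-8 does the same for SpO2.

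**Emax.** Both documents list three contrasts: Day 15 versus Day 1 within Sequence 1, Day 15 versus Day 1 within Sequence 2, and Sequence 1 versus Sequence 2 on Day 15. Neither says which postdose times, or which source (spot or continuous monitoring), feed Emax or the postdose average.

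**The concern.** The average is labelled as a value on AZD4041, but its first reading is taken before the first AZD4041 dose. That reading is also the closest of the set to the Day 1 morphine, so it represents neither a clean untreated state nor an AZD4041 state.

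The between-arm predose contrast is the only listed inferential comparison of resting respiration on AZD4041 without morphine that same day. Protocol 1.3.2 reports lower tidal volume in rats on AZD4041 alone at the highest dose. In a safety study, a built-in pull towards no difference should not be left in when it can be removed for nothing.

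A second, lesser matter is that the Emax and postdose-average windows are left open while the two morphine days have different spot schedules. The analyst would have to choose the window when programming the derivation.

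**Working it through.** The plan gives no figure of its own on this point, so there is none to reproduce.

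**1. Count of predose readings (Table 6-10).** Days 2 to 7 give 6, Day 8 gives 1, Days 9 to 14 give 6, Day 15 gives 1: 6 + 1 + 6 + 1 = 14. The reading on Day k follows k − 2 doses of AZD4041. For Day 2 that is zero doses. So 13 of 14 readings follow AZD4041, and 1/14 = 7.1% do not.

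**2. Between-arm predose contrast.** Let b be the untreated resting mean, d a constant AZD4041 effect, and m any residual morphine effect on the morning of Day 2.

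- AZD4041 arm: b + (13d + m)/14
- Placebo arm: b + m/14
- Difference: 13d/14 = 0.929d

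Residual morphine cancels in expectation because the arms are randomised. The dilution does not cancel.

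**3. Day 15 postdose versus predose, within the AZD4041 arm.** The comparator should be b + d. As defined it is b + d − (d − m)/14, so the contrast is shifted by (d − m)/14. With m = 0 this is d/14, or 7.1% of d. The sign depends on whether d or m is larger, and there is no other arm in this contrast to cancel m.

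**4. Effect of starting at Day 3.** All 13 of 13 readings then follow AZD4041. At worst, with independent readings and no between-subject variance, the standard error rises by √(14/13) = 1.038, while the expected constant effect rises by 14/13 = 1.077. The ratio of effect to standard error still improves by 1.077/1.038 = 1.038.

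**5. Readings before steady state.** Protocol 1.3.2.1 puts steady state after 6 to 8 days of dosing. Six doses have been given by Day 8 predose (8 − 2 = 6) and eight by Day 10 predose. Of the 13 readings from Day 3, between 5 (Days 3 to 7) and 7 (Days 3 to 9) are therefore on AZD4041 but before steady state.

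**6. Unequal spot schedules and Emax.** Suppose all scheduled spot readings are used: 10 on Day 1 and 11 on Day 15 for EtCO2 and SpO2. The expected maximum of 10 independent standard normals is 1.5388, and of 11 it is 1.5864. The difference is 0.0476 SD, which is the shift if morphine has no effect at all. The within-subject SD is not given. With the two baseline SDs in Protocol 6.1.9 as stand-ins, it is 0.0476 × 2.2 = 0.105 mmHg and 0.0476 × 3.88 = 0.185 mmHg.

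Simulation (200,000 replicates, exponential decay with assumed effect half-life 4 h, reading SD 1 to 3.88 mmHg, approximate paired test with n = 24) gave:

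| Assumed peak EtCO2 rise | Shift in Day 15 Emax | Two-sided type I error (nominal 0.05) |
|---|---|---|
| 0 mmHg | 0.05 to 0.18 mmHg | 0.058 to 0.059 |
| 3 mmHg | 0.00 to 0.07 mmHg | 0.050 to 0.051 |
| 5 to 10 mmHg | 0.00 to 0.03 mmHg | 0.050 |

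The Day 1 respiratory-rate line in Table 6-12 reads to 8 hours in the copy reviewed and looks incomplete, so nothing here rests on it. If it were right (9 versus 11 readings), the no-effect bound would be 0.10 SD.

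**7. Postdose average.** If the 24-hour reading is included, it lowers the Day 15 mean change by 6% to 9% for assumed effect half-lives of 12 down to 2 hours (ceiling 1/11 = 9.1%). This enters only the comparison with the predose average in step 3.

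**The case against.** The best case for leaving the text alone is that the Day 2 effect is one reading in 14, in contrasts that are only to be explored. Residual morphine on Day 2 is shared by both randomised arms, and the readings before steady state may dilute the average more than Day 2 does, which makes Day 3 look an arbitrary place to start.

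Part of this stands. The effect is small, morphine does cancel between arms, and a Day 3 start leaves 5 to 7 of 13 readings short of steady state. But those readings are at least taken on AZD4041. None of this justifies counting a reading before the first dose as AZD4041 exposure, and the cancellation does not apply to the within-arm contrast.

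A reader might also infer that the Day 15 versus Day 1 comparisons of Emax and mean postdose values are biased by a 12-hour window set against a 24-hour one. The documents do not support that:

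- The unequal windows are a collection schedule, not a stated derivation rule.
- Table 6-1 marks spot readings on Day 16, and by the study-day formula in SAP 5.1 the 24-hour reading falls on Day 16. A postdose average on Day 15 could therefore be read as excluding it.
- Mean postdose values are summarised descriptively by time point; no inferential contrast sets a Day 1 mean against a Day 15 mean.
- The Day 15 between-arm Emax contrast has identical schedules. The placebo Day 15 versus Day 1 contrast carries the same schedule difference as the AZD4041 one and so helps to show its size.
- Protocol 1.3.2.1 describes the morphine dose as supratherapeutic and chosen to make respiratory effects more likely, so a 24-hour reading would seldom be the maximum.

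**Conclusion.** The Day 2 point holds on a stated rule. One of the 14 readings in the AZD4041 predose average is taken before AZD4041. A constant effect is read at 92.9% of its size between arms, and the within-arm comparator is off by (d − m)/14. This assumes a simple average of complete predose readings and an effect that is constant once dosing starts; an effect that builds up would be diluted further. It is a minor defect that leans towards no difference between the arms.

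The window point is a clarification only. The rule is undefined. If all scheduled spot readings were used, the shift in the Day 15 versus Day 1 Emax contrasts would be at most 0.05 reading-SD for EtCO2 and SpO2, and 0.00 to 0.03 mmHg for EtCO2 with an assumed 5 to 10 mmHg morphine rise. Those figures rest on independent readings and on an assumed size, time course and within-subject SD, none of which the documents give.

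**What to change.** In SAP 9.1, define the predose average for EtCO2, SpO2 and respiratory rate as Days 3 to 15 in both arms, in both contrasts. Keep Day 2 predose in the listings and in the figure by day, marked as before the first AZD4041 or placebo dose. The cost is one reading per subject in the average and a change of one phrase. State in the text that the early readings precede steady state.

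In the same section, state whether spot or continuous readings feed Emax and the postdose average, and set a common window of 15 minutes to 12 hours on Days 1 and 15, with the 24-hour value reported descriptively. Counting the Day 2 predose reading as the Day 1 24-hour value would equalise the EtCO2 and SpO2 schedules equally well (11 versus 11). Either way the EtCO2 and SpO2 schedule difference becomes zero, with no new data and no design change. Confirm the Day 1 respiratory-rate times in Table 6-12 at the same time. Make these changes before unblinding.

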## 6.1.10. Continuous and Spot Respiratory Rate

Assessments will include continuous and spot respiratory rate as scheduled in Table 6-1. Continuous and spot respiratory rate will be monitored/measured using a capnography monitor except at Screening, Day -2, and Follow-up visit/ET where it will be measured by counting the number of breaths per minute. Respiratory rate will be continuously monitored for alarms from at least 1 hour prior to each study drug administration (prior to start of morphine IV infusion on Day 1 and Day 15) and will continue for up to 6 hours following each study drug administration (after the end of morphine IV infusion on Day 1 and Day 15), or longer if deemed medically necessary. Spot respiratory rate will be measured as scheduled in Table 6-12. Baseline

respiratory rate will be determined at 6 timepoints predose on Day 1. The baseline value will be determined by averaging the 6 readings.

# Table 6-12 Spot Respiratory Rate Recording Schedule

Spot Respi	iratory rate Recording - Scheduled Timepoints
Screen	ing
Day -2	
•	predose (at -60, -50, -40, -30, -20, and -10 minutes) and 15, 30 minutes and 1, 1.5, 2, 3, 4, 6, 8 postdose
Days 2	2 to 7: predose
Day 8:	predose (within 60 minutes) and 15, 30 minutes and 1, 1.5, 2, 3, 4, 6, 8 and 12 hours postdose
Days 9	to 14: predose
Day 15 postdos	5: predose (within 60 minutes) and 15, 30 minutes and 1, 1.5, 2, 3, 4, 6, 8, 12 and 24 hours se
Follow	/-up visit/ET

Abbreviation: ET = Early Termination

Note: On Day 1 and Day 15, predose time points are relative to start of morphine infusion and postdose time points are relative to end of morphine infusion.

The acceptable windows for respiratory rate assessments are presented in Table 6-11.

Table 6-13	Acceptable Windows for Respiratory Rate Assessments Procedures

Elapsed Time	Accepted Window
$\geq$ -1 hour and < 1 hour	$\pm 10$ minutes
$\geq 1$ hour and $\leq 24$ hours	$\pm$ 30 minutes

## 6.1.11. Laboratory Evaluations

Laboratory evaluations will be performed as outlined in Table 6-1.

The laboratory evaluations to be conducted for this study are presented in APPENDIX 6. Additional clinical laboratory tests may be performed by the medical laboratory as part of larger standard test panels (not required for subject safety).

The Investigator or delegate will assess each abnormal value to determine if it is clinically significant. Postdose clinically significant laboratory values will be reported as AEs, if applicable, as judged by the Investigator or delegate.

Only test results required by the Protocol and/or abnormal results will be entered in the clinical database and reported in the Clinical Study Report, based on report requirement.

